### 1.3. Clinical Data

Analysis of our prospective data, which was published in the *Lancet* journal *EClinicalMedicine*, suggests that patients with dyspnoea, impaired PS, decreased LOA, frailty, and borderline or poor lung function can be optimized with a standardized Prehab program, allowing them to undergo curative lung surgery safely with acceptable frequency of PPC's, LOHS and mortality (15). Despite optimisation, there remain a section of patients who remain unfit for surgery or following surgery develop complications and experience longer stays in the high dependency unit and hospital (15).

[figure not shown]
There is emerging evidence that adding a hand-held Inspiratory Muscle Training (IMT) device (Figure 2) to Prehab further optimises surgical patients and improves post-surgical outcomes by reducing PPCs which results in shorter HLOS and reduces mortality (17-20). IMT improves the strength and endurance of inspiratory muscles, namely the diaphragm and intercostal muscles through a series of breathing exercises and greatly improves the ability of individuals to take in deep breaths following surgery and expectorate and clear their airway of retained secretions more effectively, which helps reduce PPCs (17-20). IMT is analogous to strengthening one's respiratory muscles with weightlifting and inspiratory muscles are able to work for longer duration (17-20). For this study we plan to use the POWERbreathe Medic IMT device which does have a CE mark. The device is not being used outside of the purposes for which it is CE marked for this research study. The POWERbreathe medic IMT device is evidence based for a variety of medical conditions such as chronic lung disease and thoracic surgery, and is currently used by multiple patient groups, including pre operative cardiac patients as part of routine care in the Health Board. The POWERbreathe medic IMT is a single patient use device that is not decontaminated and passed onto other patients to use after the study.

On the contrary, following lung resection, to manage pleural space complications of air leak, effusion and empyema, RCT-level evidence suggests that temporarily paralysing the diaphragm (an inspiratory muscle responsible for almost 80% of inspiratory effort) with cryo-neuro-ablation of the phrenic nerve, does not significantly prolong HLOS, PPCs and mortality (21).

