**Figure 2. POWERBreathe Inspiratory Muscle Training Device**

In the presence of suggested equipoise, to obtain high level evidence for introducing IMT with Prehab into clinical practice for NSCLC surgical patients, we searched the Medline, Embase and the Cochrane library databases for English language RCTs, systematic reviews and meta-analyses published on “pulmonary rehabilitation” between Jan 1946 to May 2022 for “inspiratory muscle training”, “POWERbreathe Medic”, “inspiratory spirometry” (IS), “surgery”. Our search revealed 181 publications. 4 publications met the search question comparing IMT with Prehab and IS. Two RCTs were in cardiac surgery, one ‘pilot’ in upper gastro-intestinal surgery and one ‘pilot’ RCT in lung cancer surgery (Figure 3) (22-25).

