## 2.2. Trial Design:

This is a randomised controlled PRIMROSE trial. This trial will be single centred, as there are very few centres in the United Kingdom (UK) that deliver this highly specialised service.

Study population: Lung cancer patients with surgically resectable disease referred for pre-treatment optimization with Prehab, from the lung cancer Multi-Disciplinary Teams (MDT's) across South West Wales. Eligible patients will be randomised to the trial on a 1:1 ratio to either the intervention arm or control arm [figure 4].

Participants in group A will receive standard Prehab and training with the IMT device (POWERBreathe); participants in group B will receive standard Prehab alone.

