## Data collection

QoL data using EORTC QLQ-30 questionnaire will be collected at initial assessment (T0) and on completion of Prehab (T1) as final assessment, then post-surgery at discharge (T2) and at 1 month following surgery (T3).

Subjective outcome measures data include dyspnoea score, PS, thoracoscore, frailty index (FI), LOA and objective measures include 6-minute walk distance test (6MWD) at initial assessment (T0), after every two weeks in Prehab to assess for improvement, and finally at final assessment prior to participants proceeding to surgery (T1) (14,15,30). LOA, measured using the Borg scale of perceived exertion, will be recorded as sedentary, moderately active or active and supplemented by the 6MWD. The 6MWD will be performed using a 10m corridor instead of 30m (31). A 10 metre track along a flat corridor, will be used to measure the distance walked in metres within the 6 minutes. A 10m track was used in our previously published study and proved very effective. The American Thoracic Society guidelines state a distance of 30 metres (100 foot) should be used, however this is difficult practically. It is rare to find a 30-metre corridor in a hospital that is quiet and can allow a chair to be positioned for seated rests. A 10 metre track will be better from a health and safety point of view, as well as giving patient's privacy to focus on the self-paced walk test. These above outcome measures are already standard care for all Prehab patients (14,15).

Calculating the thoracoscore for each individual for lung resection in percentage describes the mortality risk of the individual for surgery. This is already standard operating procedure (SOP) for obtaining informed consent for lung resection surgery, and will be calculated for each participant (T0 and T1) (2,32).

The maximal inspiratory pressure (MIP) for both groups will be measured using a POWERbreathe device (Figure 2) at initial assessment (T0), on completion of Prehab (T1) and at discharge (T2). Measuring MIP is not standard practice for Prehab and will be an additional and essential outcome measure. It is required to assess the progress of each individuals improvement with the Prehab. Due consideration regarding IMT contraindications in patients to avoid harm or adverse events is included in our inclusion/exclusion criteria.

Following surgery, data on PPC's and HLOS will be collected by the researcher. This is standard practice for the prehab service.

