## 4.4. Schedule of Treatment for each visit

On initial face-to-face assessment, conducted within 5 working days of receiving the referral for Prehab, the research team will provide participants with participant information sheet and informed consent form. Informed consent to participate will be obtained. Patients can bring carers to the face-to face assessment if they wish.

**Control group:** The control group will receive a standard Prehab protocol.

**Standard Prehab protocol** is described in our previous pragmatic study published in the Lancet journal *Journal of Clinical Medicine* (15). Prehab will be provided to participants over 2–4 weeks with supervised once weekly sessions ~~with supervised two weekly sessions~~ of 70 minutes each, along with exercises for patients to carry out at home. Three weeks is an anticipated average based on published data and urgency to proceed to surgery as cancer can grow and become inoperable by six weeks. This area is much debated in the Prehab literature. Our aim is to ensure as many patients benefit with Prehab followed by lung resection surgery as possible, with broader health benefits to patients and a positive impact on their quality of life. Our previous study showed that patients can be physically optimised safely in as little as two weeks (15). However, for patients who may be slower to respond there is scope in our program for a more prolonged course of Prehab if required.

Outcome measures will be collected every two weeks on the Prehab programme by the research team, which is standard practice. As patients become eligible, they will withdraw from Prehab and proceed to surgery once a surgical date is confirmed. Management of individuals deemed unfit for surgery will be discussed at the individuals' local lung cancer MDT for consideration of alternative treatment options namely, radiotherapy, systemic anti-cancer treatment or palliative care.

**Respiratory muscle training and breathing exercises.** Both groups will receive incentive spirometry devices pre operatively. Participants will be encouraged to practice and train with the spirometer device three times daily, so can use the spirometer effectively post operatively. This is standard care as spirometers aid lung volumes and removal of secretions post operatively.

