**Cardiovascular exercises:** namely, stationary cycle ergometry and upper and lower limb resistance exercises will be performed, whilst monitoring the heart rate, blood pressure and oxygen saturations (15). The rate of perceived exertion (RPE) will be measured using the Borg breathlessness scale and used twice at every session to measure the intensity at which each patient is working and guide them to increase or decrease their effort as required.

**Home Exercise Program (HEP):** individualised home exercise programme includes daily walking plan and stair climbing exercise (15). Training enabling them to maintain activities of daily living following surgery. The HEP will be continued following discharge after surgery.

**Health education and smoking cessation advice** will be provided to all current smokers prior to surgery and support following surgery (15). Where necessary nicotine replacement therapy will be provided.

**Intervention group:** The intervention group will receive IMT in addition to a standard Prehab protocol (as above). An MIP in cmH2O, obtained at or greater than 1.5 seconds will be recorded, and the highest MIP of 3 valid breaths will be used as baseline. The IMT pressure in cmH2O will be set initially at 40% of the patients MIP. Participants will be taught to use the device in an upright position and instructed to perform six sets of six breaths with the resting times between each set of breaths reducing from 60 seconds, to 45 seconds, to 30 seconds, to 15 seconds, to 5 seconds. IMT will be used twice-daily preoperatively in the intervention group and not post operatively. Training load intensity on the IMT will be

increased preoperatively by the patient according to the rate of perceived inspiratory effort, on a modified Borg scale.

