## 11. Intellectual Property

The research question is based upon previous published work and a gap in the literature, identifying a new hypothesis. Appropriate credit to previous published work is provided in the reference section.

All manufacturer names and trademark of equipment are listed below to ensure compliance with trademark laws:

POWERbreathe is the inspiratory muscle trainer to be used in this trial

The CI has obtained permission to use the European Organization for Research and Treatment of Cancer (EORTC) QLQ – C30 QOL questionnaire by completing the online Academic User Agreement.

As this trial is not the development of a device, no intellectual property (IP) will be produced.

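### MIP is measured in both arms on the make of device that only the IMT arm trains with, so part of a between-arm difference may be familiarity rather than strength

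*Protocol*

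**What the plan says.** Section 2.4.1 (Data collection) fixes the instrument: "The maximal inspiratory pressure (MIP) for both groups will be measured using a POWERbreathe device (Figure 2"). It schedules the measurement at T0, T1 and T2, as does the schedule in section 4.5, and describes MIP as an additional and essential outcome. Section 7.2 lists it among the secondary efficacy endpoints.

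The caption of Figure 2 reads "POWERBreathe Inspiratory Muscle Training Device". Section 1.3 cites the same figure when it speaks of "adding a hand-held Inspiratory Muscle Training (IMT) device (Figure 2) to Prehab", and section 11 states that "POWERbreathe is the inspiratory muscle trainer to be used in this trial".

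The arms differ in exposure to it. Section 4.4 says "IMT will be used twice-daily preoperatively in the intervention group and not post operatively", as six sets of six breaths per session. Section 2.2 says "participants in group B will receive standard Prehab alone". The breathing device that the arms share is a different one: "Both groups will receive incentive spirometry devices pre operatively" (section 4.4).

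The only measurement rule is in the intervention-group paragraph of section 4.4. It asks for a pressure obtained at or beyond 1.5 seconds and adds that "the highest MIP of 3 valid breaths will be used as baseline".

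**The concern.** A maximal inspiratory pressure depends on the patient's effort and technique as well as on muscle strength. If one arm has used the same make of device for weeks and the other has met it only at the baseline test, randomisation balances familiarity at T0 but not at T1. Training stops at surgery, but familiarity gained before it may still be present at T2.

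The protocol's hypothesis (section 1.4) is that IMT strengthens the inspiratory muscles and thereby lowers the risk of pulmonary complications. MIP is the only measure in the section 4.5 schedule that addresses inspiratory muscle strength directly; FEV1 and TLCO are taken at T0 only. A between-arm MIP difference is thus the natural evidence for the first link in that chain, and as planned it cannot separate strength from familiarity. Unequal familiarity cannot be removed in the analysis afterwards, so it has to be reduced when the measurement is taken.

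**Working it through.** The plan gives no figure for this point, so there is none to reproduce. The check has three parts.

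**1. Is the measuring device the training device?**
- Section 2.4.1 measures MIP on a POWERbreathe and cites Figure 2.
- Section 1.3 and the caption identify Figure 2 as the trainer. Section 11 names POWERbreathe as the trial's trainer.
- No other pressure meter is named anywhere.

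The make is the same. Whether the test uses the same unit is not stated. Section 1.3 says each Medic trainer is for a single patient, so what the controls breathe through is left open.

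**2. How far does exposure differ by T1?**
- Intervention arm: 6 sets × 6 breaths × 2 sessions = 72 breaths a day. Prehab lasts 2 to 4 weeks: 72 × 14 = 1,008 and 72 × 28 = 2,016 breaths at full adherence. Section 2.1 anticipates that 80% of participants will adhere, so the average may be lower.
- Control arm: no training on the device. The only contact written in the plan is the MIP test itself.
- No practice effort, sham device or familiarisation session is described for controls.

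These counts show how unequal the contact with the device is. They do not count rehearsals of the test, because training starts at 40% of MIP and the test is maximal.

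**3. What could it do to the comparison?** The documents give neither an SD for MIP nor a familiarity effect, so this part is an illustration under assumed values.

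Inputs: 50 per arm and two-sided 0.05 (section 2.4.2); true strength difference 0; assumed familiarity shift *b* in SD units in the IMT arm.

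Standard error of the difference in SD units: √(2/50) = 0.20.

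Chance of a significant result: Φ(b/0.20 − 1.96) + Φ(−b/0.20 − 1.96).

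| Assumed shift *b* (SD) | b/0.20 | Normal approximation | Two-sample t test |
|---|---|---|---|
| 0 | 0 | 5.0% | 5.0% |
| 0.1 | 0.5 | 7.9% | 7.9% |
| 0.2 | 1.0 | 17.0% | 16.8% |
| 0.4 | 2.0 | 51.6% | 50.8% |

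Example for 0.2 SD: Φ(1.0 − 1.96) + Φ(−1.0 − 1.96) = 0.1685 + 0.0015 = 0.170.

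The rows run from no inflation to a large one. Nothing in the documents says which row applies.

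**The case against.** The case for leaving the plan alone has several parts.

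- **Training is not the test.** A reader might infer that the IMT arm rehearses the MIP test more than a thousand times. Section 4.4 does not support this. Training is repeated resisted breathing that starts at 40% of MIP, with load raised by perceived effort; the test is a maximal effort, best of three. This objection stands. What remains is familiarity with the device and with a related manoeuvre.
- **The unit may be separate.** Section 2.4.1 says only that a POWERbreathe is used, so a dedicated measuring unit of that make would fit the wording. This also stands, although the reference to Figure 2 points to the trainer. A separate unit would reduce the overlap without giving controls any practice.
- **Controls do practise breathing.** Both arms are encouraged to use an incentive spirometer three times a day. This narrows the gap in general inspiratory practice. It does not close it for the test device, and section 2.4.1 itself distinguishes spirometry-based training from POWERbreathe training.
- **The rule's placement proves little.** The 1.5-second, best-of-three rule may sit under the intervention group simply because baseline MIP sets the training load. Nothing says controls are tested differently, and that should not be inferred. The text nevertheless leaves the rule unstated for controls and, in both arms, for T1 and T2.
- **A few practice efforts cannot match weeks of use.** This is correct. The remedy reduces the imbalance and does not remove it, which is why the wording of the report also has to change.
- **MIP is secondary, and no mediation analysis is planned.** This stands and limits the importance of the point.

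**Conclusion.** The point holds as a modest but real weakness in one secondary endpoint. The make of device used for the test is the one that only the IMT arm trains with, no common measurement rule is written for both arms and all visits, and controls have no familiarisation. Part of a between-arm MIP difference at T1 or T2 may therefore be familiarity.

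The size is unknown. The range of about 5% to 51% for a significant difference with no strength effect rests wholly on assumed shifts of 0 to 0.4 SD, 50 analysed patients per arm and a comparison of two means. The lower end means no problem at all.

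Two stronger readings go beyond the documents. One is that a MIP gain in the IMT arm would be mostly or certainly practice: no passage supports any particular share, and a true strength gain is fully compatible with the same data. The other is that the trial's main result is compromised: pulmonary complications are recorded independently of MIP, so the primary comparison is untouched.

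**What to change.** In sections 2.4.1 and 4.4, state one MIP procedure for both arms at T0, T1 and T2:

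- a fixed number of unrecorded practice efforts, the same in each arm and at each visit;
- then the highest of three valid efforts held for at least 1.5 seconds, which extends the existing baseline rule to controls and to the later visits;
- taken on a measuring unit that is not the patient's own trainer, with that unit named.

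State also that a between-arm MIP difference will be reported as supportive evidence of mechanism and that residual familiarity cannot be excluded.

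The cost is a few extra minutes at each MIP visit and a short change of wording. The training regimen, the sample size and the primary analysis stay as they are. The change should be made before further MIP measurements are taken, because mixing two procedures within the trial would add a difference of its own.

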#### **2.4.2 Analysis Plan**

Our aim is to evaluate the impact of thoracic Prehab with IMT compared to standard Prehab in reducing post operative pulmonary complications following surgical resection in lung cancer patients in a RCT.

The analysis will include descriptive data (means and standard deviation) on all outcomes collected, including levels of missing data, leading to the calculation of clinically important differences. Descriptive statistics will be used to summarise participants' baseline characteristics and outcome measures.

Statistical analyses will be performed using SPSS statistical software, version 20.0 (IBM Corporation, Armonk, NY, USA). Two-sided significance tests will be used ( $\alpha \leq 0.05$ ). Data will be presented as mean and standard deviation (SD), or median and interquartile range (IQR) for variables with a skewed distribution. Differences between groups in categorical variables will be tested with Chi square or Fisher's exact test. For continuous data the student's t test or the Mann-Whitney U test will be used. The Wilcoxon signed rank test will be used to compare MIP and QoL at T0 and T1 and T3. Relative risk will be calculated for post operative pulmonary complications (PPCs) graded 1-V using the Clavien Dindo classification and impact of IMT on the study group compared to the control group. Assuming a 36.7% incidence of PPC after surgery in the control arm and using a significance level of 0.05 and a power of 80%, 50 patients are required in each arm of the study for analysis."

#### **2.4.3. Project statistician / methods expert**

Statistical analyses will be performed using SPSS statistical software, version 20.0 (IBM Corporation, Armonk, NY, USA) by the chief investigator who is familiar with the use of this software and has previously published data in the lancet journals eclinical medicine (15).

### 3. Subject Selection

#### 3.1. Number of subjects and subject Selection

Daily screening of new prehab referrals by the principal investigator or research team, using a consecutive sample approach will be used for participant recruitment. This means selecting all patients who meet the eligibility criteria. Patients over a 12-month period (from January 2025) will be approached to gain consent. However, if recruitment numbers are an issue the study will be extended by six months.

#### 3.2. Inclusion Criteria:

Lung cancer patients with surgically resectable disease who are referred for pre-treatment optimization with Prehab from the lung cancer Multi-Disciplinary Teams (MDTs). The referral criteria for Prehab is one or more of the following (15):

- $\geq 1$  Medical Research Council (MRC) dyspnoea score
- $\geq 1$  World Health Organization (WHO) performance status (PS)
- Age  $\geq 70$  years
- Frailty index  $>3$
- Borderline or poor pulmonary function (forced expiratory volume in one second (FEV1)  $< 50\%$  or diffusion capacity for carbon monoxide (DLCO)  $< 50\%$ )
- Sedentary patients despite having adequate FEV1 or DLCO

Additionally:

- Surgical resection can be performed, including endobronchial excision of tumour, or lobectomy, segmental resection, pneumonectomy or wedge resection, either via a minimally invasive approach or a standard thoracotomy approach
- Patients will be included in the trial if they are capable of providing verbal written consent for Prehab, and written consent for undergoing surgical resection for lung cancer
- Are over 18 years of age
- All patients will be considered regardless of their baseline respiratory muscle strength

### 3.3. Exclusion Criteria:

- Inclusion criteria not met
- Patients who have undergone recent abdominal surgery and those with an abdominal hernia
- Patients diagnosed with other cancers namely, patients with metastatic lung cancer, mesothelioma, sarcoma, mediastinal tumours, or benign diseases
- Patients who decline Prehab
- Patients who do not consent to Prehab, do not attend or have died prior to commencing Prehab. Patients who do not consent to surgery.
- Patients with a high cardiovascular risk for Prehab and awaiting investigations or interventions (including unstable angina and syncope)
- Patients with a serious concomitant disorder that would compromise patient safety during Prehab
- Patients with a history of spontaneous pneumothorax and/or evidence of large bullae on radiological imaging
- Patients who have suffered from or likely to suffer from costochondritis
- Patients with marked osteoporosis with history of rib fractures
- Patients with pulmonary hypertension
- Patient with a perforated ear drum
- If a participant is involved in a study similar, with potential to cause bias or conflict of interest then they will be excluded
- Patients with worsening heart failure signs and symptoms after IMT

To prevent the transmission of respiratory infections, the research team will advise patients not to share the device with family members. If patients are suffering from a cold, sinusitis or respiratory tract infection they will be advised not to use the device until their symptoms have resolved.

Participants who do not understand written and/or spoken English can access a translator through the health board.

The research team will collect a list of patients that decline to participate in the trial, to assess recruitment rates at the end of the study.

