**STUDY SUMMARY/SYNOPSIS**

TITLE	A randomised controlled trial to evaluate the impact of thoracic PRehabilitation with Inspiratory Muscle tRaining cOmpared to Standard prEhabilitation in surgical lung cancer patients.
SHORT TITLE	PRIMROSE Trial
Protocol Version Number and Date	Standard Protocol Version Number 3.5 and date 03/02/25
Methodology	Type of study: randomised control trial
Study Duration	Two years
Study Centre	Cardiothoracic centre, Morriston Hospital
Objectives	To compare inspiratory muscle training (IMT) with standard Prehabilitation (Prehab) to Prehab alone, in lung cancer patients for surgery.
Number of Subjects/Patients	One hundred and thirty-four patients will be recruited for the study (67 for each arm) and with an anticipated attrition rate of 20-25%, one hundred patients will finally be studied.
Main Inclusion Criteria	
All adult lung cancer patients > 18 years diagnosed or suspected of non-small cell lung cancer (NSCLC) with surgically resectable disease, who are referred for pre-treatment optimization with Prehab from the lung cancer Multi-Disciplinary Teams (MDTs) across South West Wales (Swansea lung MDTs, the Hywel Dda lung MDTs and Princess of Wales lung MDT).
 
Lung cancer patient are referred for pre-treatment optimization with Prehab if they meet the following referral criteria: <math>\geq 1</math> Medical Research Council (MRC) dyspnoea score; or <math>\geq 1</math> World Health Organization (WHO)

	
performance status (PS); age <math>\geq 70</math> years or frailty index <math>>3</math>; borderline or poor pulmonary function (forced expiratory volume in one second (FEV1) or diffusion capacity for carbon monoxide (DLCO) <math><50\%</math>); sedentary patients despite having adequate FEV1 or DLCO. Patients will be included in the trial if they are capable of giving consent to participation and aged 18 and over.
 
Additionally, patients who have no contraindications to IMT use.

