## 2. Objectives and Design

### 2.1. Trial Objectives

**Primary Objective:** A randomised controlled trial to evaluate the impact of thoracic PRehabilitation with Inspiratory Muscle tRaining cOmpared to Standard prEhabilitation in surgical lung cancer patients [PRIMROSE Trial].

**Recruitment rate:** The study aims to recruit 134 patients for randomisation over twelve months, with 67 randomised to the intervention group and 67 to the control group (6).

**Retention rate:** These are high-risk patients and a high attrition rate in this population is considered normal. We anticipate the retention of 50 patients in each arm following 1:1 randomisation, and is based on our previous study (15), which showed that following assessment, 6.8% NSCLC patients fail to attend Prehab and 1.1% died prior to commencing Prehab. Likewise, following Prehab, 75.8% patients are ready to proceed with surgery. The attrition rate is an estimate and is anticipated attrition to be 20%-25%.

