### 3.4. Criteria for Premature Withdrawal

Participants will be withdrawn from the study for the following reasons:

- Participants are no longer considered suitable for surgical lung resection by the MDT. Other treatment options may be considered more prudent such as radiotherapy or systematic anticancer treatment or best supportive care.
- The participant decides they no longer wish to be part of the study or have decided against surgical resection
- The research team decide it is unsafe for the participant to continue due to medical, safety and regulatory concerns. This includes adverse cardio-respiratory events relating to the patients physical conditioning as assessed by the cardiothoracic physiotherapists
- If the participant becomes lost to follow-up as deemed by the research team
- If the participant loses their capacity during the study period (including death)
- A significant increase in post-surgical mortality

Patients have the right to refuse study participation.

If a participant loses capacity to consent or withdraws consent, they will be withdrawn from the study. Identifiable data already collected with consent would be retained and used in the study. No further data would be collected or any other research procedures carried out on or in relation to the participant.

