## 4.3. Randomisation Procedures (if applicable)

Participants will be randomised 1:1 to either the intervention or control group without stratification using an online randomisation service, 'Sealed Envelope' ([wwwsealedenvelope.com](http://wwwsealedenvelope.com)) (34).

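### Section 3.3 lists as exclusions events that the protocol itself places after allocation, one of which only an IMT-arm patient can meet

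*Protocol*

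**What the plan says.** Section 3.3 of the protocol lists among its exclusion criteria "Patients who do not consent to Prehab, do not attend or have died prior to commencing Prehab. Patients who do not consent to surgery", and further down "Patients with worsening heart failure signs and symptoms after IMT".

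Section 2.1 expects 50 patients to be retained in each arm after 1:1 allocation. It rests this on an earlier study in which, after assessment, "6.8% NSCLC patients fail to attend Prehab and 1.1% died prior to commencing Prehab", and 75.8% were ready for surgery after Prehab. Section 1.1 turns the expected 25% loss into 134 recruited and 100 studied.

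On timing, section 4.3 says "Participants will be randomised 1:1 to either the intervention or control group without stratification" and names no visit or moment. Section 4.4 takes consent at the initial assessment and gives IMT before surgery to the intervention group only. Section 4.12 promises an intention-to-treat analysis of all patients, as protection against attrition bias when patients withdraw or are withdrawn.

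Two other items bear on the point less directly:
- Section 3.4 makes it a withdrawal reason if participants "no longer wish to be part of the study or have decided against surgical resection", while 3.3 excludes those who do not consent to surgery.
- The synopsis admits patients "diagnosed or suspected of non-small cell lung cancer (NSCLC) with surgically resectable disease", while 3.3 excludes "Patients diagnosed with other cancers namely, patients with metastatic lung cancer, mesothelioma, sarcoma, mediastinal tumours, or benign diseases".

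**The concern.** An eligibility criterion should be decidable when the patient is randomised. If it can be met only later, a site following the list literally may declare an allocated patient ineligible and remove that patient from the trial. Randomisation no longer protects the comparison if such removals depend on the arm. The heart-failure item is of that kind: control patients receive no IMT, so only the IMT arm can lose patients under it, and those lost are patients who did badly on the device. Prehab staff know the allocation, since 4.10 blinds only the data analysts and the post-operative physiotherapists.

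Non-attendance and death before Prehab raise a different problem. Under 3.3 they are screen failures who were never in the trial. Under 2.1 they are losses from the 134 randomised. The choice decides how many of the 134 reach surgery and can contribute a post-operative pulmonary complication (PPC) outcome.

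**Working it through.** **The sections side by side**

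1. IMT is given before surgery to one arm (4.4), so allocation must precede it. An event defined as following the trial's IMT therefore comes after allocation and cannot occur in the control arm.
2. Non-attendance and death before Prehab are exclusions in 3.3. In 2.1 they occur after assessment and help justify the fall from 67 to 50 per arm. The same patient cannot be both never eligible and a post-randomisation loss. Because 4.3 gives no time point, nothing settles which is meant.
3. Section 4.12 covers patients who withdraw or are withdrawn. It does not say what happens to a randomised patient later found to meet an exclusion criterion.

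**The plan's own figure**

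Inputs: 100 patients to be studied and 25% attrition (1.1). 100 / (1 − 0.25) = 133.3, or 50 / 0.75 = 66.7 per arm, rounded up to 67. The stated 134 reproduces.

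**Patients classed both ways**

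6.8% + 1.1% = 7.9%. 134 × 0.079 = 10.6, about 11 patients (5.3 per arm).

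**Patients reaching surgery**

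Assumption: the 75.8% in 2.1 refers to patients who start Prehab. The protocol does not give the denominator.

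- Randomised after the 7.9% losses: 134 × 0.758 = 101.6, about 102 (51 per arm).
- Randomised before them: 134 × 0.921 × 0.758 = 93.5, about 94 (47 per arm). The total loss is 1 − 0.921 × 0.758 = 30.2%, above the 20% to 25% planned.

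If the 75.8% refers instead to all assessed patients, randomising at assessment leaves 101.6. Randomising after the losses leaves 101.6 / 0.921 = 110.3. The planned 100 is then met either way.

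**Power, on the first reading**

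The control rate is 36.7% with alpha 0.05 two-sided (2.4.1, 2.4.2). The text gives no intervention-arm rate. With the unpooled normal formula, 50 per arm and 80% power correspond to about 13.2% to 13.3%, so 13.3% is used here as an assumption, with a range around it. Power below is that of the uncorrected chi-square test, by exact binomial enumeration.

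| Assumed IMT-arm rate | 47 per arm | 51 per arm |
|---|---|---|
| 11% | 85.6% | 88.5% |
| 13.3% | 76.3% | 80.1% |
| 15% | 68.4% | 72.5% |

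The difference is about 3 to 4 percentage points throughout.

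**The case against.** The best defence is section 4.12. If all patients are analysed by intention to treat, a late exclusion has no effect on the analysis. This mitigates the concern but does not close it, because the sentence is tied to withdrawals, and an excluded patient can be argued never to have belonged to the analysed population.

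Second, patients who never attend or who die before Prehab have no operation and so no PPC outcome. Calling them excluded rather than lost removes no observed outcome. That stands: for these patients the problem is one of counting, and the bias argument rests on the heart-failure item.

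Third, the heart-failure item might be meant as a history of such worsening with earlier IMT. The text does not say so, and that reading would also need rewording.

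A reader might infer more than this, and the documents do not support it:
- *That 3.2 demands signed surgical consent at entry.* The item mentions "written consent for undergoing surgical resection for lung cancer", but asks only that the patient be capable of giving it. That can be judged at entry.
- *That 3.3 and 3.4 contradict each other on refusing surgery.* They can be two stages: refusal stated at screening, and a later change of mind.
- *That benign or other pathology at resection strikes patients off once the outcome is known.* No section says so. Section 4.2 validates diagnosis and stage at screening, for suspected as well as diagnosed cancer. The most that can be said is that such findings may emerge after allocation and the protocol does not state that they are then ignored. A loss of power from this source cannot be derived from the documents.

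**Conclusion.** The point holds in a limited form. Section 3.3 contains one criterion that, for the trial's own IMT, only an allocated intervention-arm patient can meet. It contains two more that 2.1 treats as losses after randomisation. With no time point in 4.3 and an intention-to-treat statement confined to withdrawals, the protocol permits randomised patients to be ruled ineligible, in one case from one arm only. Refusal of surgery and final pathology are secondary: they may arise late, but they can also be settled before allocation.

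The overlap concerns about 11 of 134 patients. The difference of 94 against 102 patients, and of about 76% against 80% power, depends on applying the 75.8% to those who start Prehab and on the assumed 13.3% rate. Across assumed rates of 11% to 15% the power level moves much more than the gap does. The protocol gives no basis for the number of patients who might meet the heart-failure item, so the size of any bias from it cannot be stated. Extra recruitment would not repair such a bias, so the wording is worth correcting even though the effect on power is modest.

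**What to change.** 1. **Section 4.3:** state that randomisation takes place after consent and the T0 measures, at the first attended Prehab session. Non-attendance and death before Prehab are then true pre-randomisation exclusions and should leave the attrition basis in 2.1.
2. **Sections 3.2 and 3.3:** limit eligibility to facts known at randomisation. Refusal of surgery in 3.3 should mean refusal stated before randomisation, with later refusal left to 3.4. Diagnosis should mean the working diagnosis at screening, suspected or confirmed, as in the synopsis.
3. **Heart failure after IMT:** take this item out of the eligibility list and reconcile 3.3, 3.4 and 7.3 on how such an event is handled. The care rule is for the clinicians, and no particular rule is proposed here.
4. **Section 4.12:** state that no randomised patient is removed from the analysis because an exclusion criterion or a final pathology result comes to light later.

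The cost is amendment wording, with no extra patients or procedures. The one practical downside is that IMT may start slightly later when the first Prehab session falls after the assessment visit. Prehab lasts only 2 to 4 weeks with weekly supervised sessions (4.4), so the team should weigh this when fixing the moment of randomisation.
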